**Purpose:**

Healthy Aging Resources to Thrive (HART) intervention focuses on reducing sitting time by standing more and breaking up prolonged bouts of sitting throughout the day. Because older adults with obesity rarely engage in physical activity, helping them sit less throughout the day could be a meaningful, but untested, health-promoting behavior. We will target a group with high prevalence of cardiometabolic conditions in which we have the opportunity to see the largest improvement in biomarkers related to cardiometabolic risk. We will conduct an efficacy randomized controlled trial to determine whether a sitting reduction intervention, improves behavioral and health outcomes to a greater extent than an attention-control group. The primary end point is 6 months. but participants randomized to the i-STAND intervention will be re-randomized at 6 months to either receive no further contact or a booster session intervention. Everyone will be followed until 12 months after baseline.

**2022 BUDGET CUT UPDATE:** As of March 31, 2022, participants randomized to the i-STAND intervention will no longer be re-randomized at 6 months. We will no longer follow participants to the 12-month timepoint and will end all activities after the 6-month timepoint.

The specific aims of the study are to:

Aim 1: Determine the efficacy of i-STAND to improve primary and secondary outcomes at 6 months.

Our primary outcomes are change from baseline in mean daily sitting time and systolic and diastolic blood pressure. We will compare group means for our primary outcomes between participants randomized to i-STAND versus attention control ("Healthy Lifestyles") at 6 months. Secondary outcomes include cardiometabolic biomarkers (HbA1c,), weight, height, and physical function.

Aim 2: Determine the maintenance of sitting and blood pressure reductions over 12 months.

We will then assess differences in primary outcomes at 12 months in the two i-STAND groups: with and without the booster intervention.

**Hypothesis 2:** i-STAND participants randomized to receive booster sessions will have reduced sitting time and improved cardiometabolic risk factors at 12 months compared to i-STAND participants receiving no further intervention and compared to the Healthy Lifestyles/attention control participants.

**2022 BUDGET CUT UPDATE:** As of March 31, 2022, we are cutting Aim 2 so as to conserve funds to focus on Aims 1 and 3.

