**By mail and phone:**

Potential participants will be mailed a letter describing the study with a phone line to call if they do not wish to participate. Those who do not decline will be called by our Survey Research Program staff. The Survey staff will obtain oral consent to be screened for eligibility by phone, answer any questions about the study, screen for eligibility, and, if eligible, obtain oral consent to wear the activPAL prior to the Baseline visit. Those who consent to participate in this stage will be scheduled by the Survey team for their Baseline measurement session. At 6 and 12 months, participants will receive an activPAL device and questionnaire by mail, and will participate in a follow-up in-person measurement visit (see In Person section below).

For participants in both the intervention i-STAND group (Group A) and the Healthy Lifestyles group (Group B), additional activPAL measurements will be collected (via mailed activPAL) at 3

months; for those *re-randomized* to the i-STAND booster group, they will also receive an activPAL at 9 months via mail. Neither the 3 or 9 month activPAL wears will be followed by an in-person visit. Reminder letters for upcoming in-person visits will be sent one-week prior to visit by the Research Specialist. For each period that an i-STAND subject wears an activPAL device, they will also receive a copy of their feedback chart via mail or in-person (depending on timepoint). If requested by the participant, reminders may be sent by email. Email addresses will be collected on the Contact Sheet if this request is made. Also see Supplement B.

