## Data, sources, and date range

The following table shows how outcomes data will be collected

Source (specify) (i.e., from KPWA, or from an existing or previous study)	Key Information/Description of Variables	Date Range
---	--	------------

activPAL activity monitor	PRIMARY OUTCOME 

• Change in mean daily sitting at 6 months

	Baseline to 6-months
ORIGINAL COHORT: In-person measurement visit at KPWHRI  COVID-19 UPDATE AND NEW REMOTE COHORT REMOTE MEASUREMENT	PRIMARY OUTCOME 

• Change in systolic and diastolic blood pressure

	Baseline to 6-months
In-person measurements collected at clinic visit at KPWHRI  COVID-19 UPDATE AND NEW REMOTE COHORT: REMOTE MEASUREMENT OF WEIGHT	SECONDARY OUTCOMES 

• Change in HbA1c (Original Cohort only)

• Change in Weight

	Baseline to 6 months
In-person measurements collected at clinic visit at KPWHRI  COVID-19 UPDATE and REMOTE COHORT: REMOTE MEASUREMENT OF WEIGHT and BP	OTHER EXPLORATORY OUTCOMES for i-STAND BOOSTER ONLY 

• Change in HbA1c (original cohort only)

• Change in Weight

• Change in systolic and diastolic blood pressure

	Baseline to 12 months
activPAL activity monitor	OTHER EXPLORATORY OUTCOMES for i-STAND BOOSTER ONLY 

• Change in time spent sitting or lying down

• Change in step counts

	Baseline to 12 months
Participant questionnaire	OTHER EXPLORATORY OUTCOMES 

• Change in quality of life

• Change in depressive symptoms

	Baseline to 6 months

	
 
• Change in physical function
 
	
VDW	
Various chronic conditions (e.g. diabetes, cardiovascular conditions); lab values for HbA1c, cholesterol; blood pressure; blood pressure medications; height and weight; medical events (e.g. falls, hospitalizations, heart attack, stroke, blood clots); and, healthcare costs.
	
One year prior to first Study Visit date to the end of the study for up to 5 years after the study ends, no later than June 1, 2028

**2022 BUDGET CUT UPDATE:** As of March 31, 2022, neither the i-STAND cohort nor the control cohort will have a 12-month assessment to collect the outcomes listed in the table above. To be as clear as possible - those items have been highlighted in green.

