  - a. All i-STAND participants will receive one more in-person session and 8 follow-up phone calls (10 contacts total) from their health coach over 6 months. All participants will also be sent an activPAL to wear, as well as a survey, at the mid-point (Month 3) and will receive a \$20 incentive for wearing the activPAL at month 3. All participants will receive a reminder phone call from the RS to confirm receipt of the packet containing the activPAL and the survey. If the packet was not received, the RS will resend another packet. At the 3-month mark, health coaches will also collect satisfaction data on use of the devices. This information will be collected over the phone and input into REDCap by the coaches, so as to avoid contaminating the survey data collected by the blinded research specialists, who will be managing the primary survey distribution and data collection.
  - b. All Healthy Lifestyle Control Participants will receive 9 follow-up phone sessions after their initial in-person session (10 contacts total). Each call will cover a topic of interest to the participant (see Table 4). Relevant content from the Healthy Living workbook will be briefly reviewed and goals will be set. Follow-up calls will check-in with prior calls. The calls will occur every 2-3 weeks over the first 6 months of the study.
  - c. COVID-19 UPDATE: both i-STAND and Health Lifestyle participants will be offered, using an Addendum to Consent oral agreement, the option of additional coaching calls beyond the 10 sessions to occur on a monthly basis. See page 15 of this protocol for details and see the Addendum Consent for script. 3-month assessments will also still be mailed. A study RS will assemble packets with charged activPALs and participant surveys at their home and mail to participants via the USPS. Study RS has sanitation procedures that are used at the office that will also be used at home in assembling packets (gloved, wipes, etc). Participants will mail the packets back to KPWHRI and a study RS will be checking our mailbox once a week for returned devices/surveys.
  - d. All participants (i-STAND and Healthy Lifestyles control group) will attend a 6-month measurement visit. A few weeks prior to the visit and to mailing the activPAL device to the participants, the RS will call the participant to ensure we have accurate contact information and to remind them of the upcoming timepoint. If the participant has

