**ORIGINAL (in-person) COHORT**

Additional information about assessments and measurements at in-person visit (baseline, 6 and 12 months):

**Cardiometabolic biomarkers:** We will measure HbA1c. To measure HbA1c, we will obtain a capillary whole blood sample obtained by finger prick, collected in a toothpick-sized capillary tube, and analyzed immediately using the Siemens DCA Vantage Analyzer. It performs a CLIA-waived HbA1c test that is IFCC and NGSP-certified.

Potential incidental findings may include a discovery that the participant has Diabetes. If this is discovered, the physician on call will notify the research specialist who will advise the participant to meet with their primary care provider as soon as possible.

**Weight, Height, Waist.** Weight will be measured using a calibrated Seca Digital weight scale. Height will be measured using a calibrated Seca Digital Stadiometer. Waist circumference will be measured twice at the superior border of the iliac crest and the average of two measurements used.

**COVID-19 UPDATE:** remote weight measurement at 6 and 12-months (until normal business resumes) will be collected as available and depends on the participant having a scale at home. Waist circumference will be collected using a Medline brand paper measuring tape which will be sent ahead of time to participants along with instructions on how to take an accurate measurement.

**Blood Pressure:** We will measure blood pressure (systolic and diastolic) three times to ensure accurate results. BP will be measured using an OMRON Digital BP Monitor with Intellisense. Model HEM907XL. We will also advise participants to avoid caffeine, tobacco and exercise in the 30 minutes

prior to the visit to ensure accuracy. After consent and when scheduling the baseline visit, we will ask the participant for height and weight so we can plan to send them the right size cuff with their BP monitor.

**COVID-19 UPDATE:** Until we return to normal business, we will be mailing Omron 3-Series BP7100 monitors (along with cuff and instructions on use) from a third party vendor (pending oral consent from the participant). These were recommended as a good option for home monitoring by Co-I [name] who has an expertise in blood pressure. Study measurement of blood pressure using these devices will be conducted during a phone call with the study Measurement RS, allowing for verbal instructions and questions from participants about the proper use of the device.

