**Aim 1: Determine the efficacy of i-STAND to improve primary and secondary outcomes at 6 months.**

*Primary Outcome Analysis:* Our primary outcomes are change from baseline in mean daily sitting time and systolic and diastolic blood pressure (described in Section C12). We will compare group means for our primary outcomes between participants randomized to i-STAND versus attention control using linear regression with generalized estimating equations (GEEs) including both outcome time points at 3 and 6 months. GEE is used to account for multiple outcomes measured on the same study participant along with relaxing the normality assumption that standard linear regression methods require. We will adjust for baseline covariates including participant age, sex, physical function, and respective baseline outcomes with other covariates that are imbalanced in preliminary analyses. If dropout is above 15%, we will employ imputation techniques to address missing data issues. However, our focus will be on minimizing dropout rates. Analyses for secondary outcomes including lipids, fasting glucose, weight, and waist circumference will be similar, adjusting for respective baseline outcomes in the analysis. *Aim 2: Determine the maintenance of sitting and blood pressure reductions over 12 months.* We will conduct a sequential series of analyses using a similar statistical framework as outlined for Aim 1, but using 12-month follow-up data. We will first run a regression model with three groups (attention control, i-STAND no boosters, and i-STAND with boosters) including baseline covariates as outlined above. We will then

assess differences in primary outcomes at 12 months in the two i-STAND groups: with and without the booster intervention. If a significant difference in a given primary outcome is found in sitting time at 12 months between the i-STAND booster versus no booster groups (Scenario 1), we will further compare the i-STAND booster and no booster groups to the attention control group. Scenario 1 assessments will determine if i-STAND with boosters is better than i-STAND without boosters and if either or both I-STAND groups are better than attention control at 12 months.

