**Power calculations.** Our sample size of 284 ensures 90% power to detect a difference in the reduction of sitting time between i-STAND and attention control of 41 minutes at 6 months (primary time point). Given our pilot results and i-STAND's long-term goal target of a 2 hour reduction in sitting time, a difference in sitting time reduction of 41 minutes is achievable. We assumed a standard deviation (SD)

in change in sitting time of *97 minutes/day based on I-STAND pilot RCT data*, a pooled sample t-test, and a 15% loss to follow-up under which we would observe 241 participants at 12 months. *Further, this sample size provides 90% power to detect a difference of 6.2 mmHg change in systolic (14.7 SD) and 4.0 mmHg change in diastolic (9.5 SD) blood pressure. We are powered for comparable reductions in blood pressure as those observed in walking and exercise interventions (5-10 change in systolic and 1-6 mmHg change in diastolic blood pressure). Therefore, we are powered to achieve a minimal clinically important difference for blood pressure outcomes.*

For Aim 2, we will have 90% power to detect a 58-minute difference in sitting time between i-STAND with boosters compared to i-STAND without boosters at 12 months. Further, given Scenario 2 in which i-STAND boosters is not different than i-STAND without boosters we will have 90% power to detect a 41-minute difference in sitting time with combined I-STAND groups. Given Scenario 1, in which i-STAND with boosters is significantly different from i-STAND without, at 12 months, we will have 90% power to detect a 50-minute difference in sitting time between either i-STAND group and the attention control. *For blood pressure outcomes, we have 90% power to detect an 8.8 mmHg change in systolic blood pressure and 5.7 mmHg change in diastolic blood pressure when comparing i-STAND groups (booster vs. no booster) at 12 months.* Therefore, this study is well powered to address all aims.

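### Does the primary GEE, which takes both months 3 and 6 as outcomes, fail to deliver the month-6 comparison?

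*Combined protocol and SAP*

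**What the plan says.** Section 5.a (Data Analysis, Aim 1) compares group means on the primary outcomes "using linear regression with generalized estimating equations (GEEs) including both outcome time points at 3 and 6 months". The adjustment variables it lists are baseline ones. The only interactions named in the plan are the baseline moderators of Aim 3.

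The time point is stated elsewhere. Section 1 (Purpose) says "The primary end point is 6 months", and its account of Aim 1 places the comparison of group means at 6 months. The outcomes table in Section 5 lists "Change in mean daily sitting at 6 months" and gives baseline to 6 months as the date range for blood pressure. The Aim 1 heading ends at 6 months. The power paragraph refers to "41 minutes at 6 months (primary time point".

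The cohorts differ at month 3. For the Original cohort (100 planned), Section 5 says "All participants will also be sent an activPAL to wear, as well as a survey, at the mid-point (Month 3", and Section 4.j adds "Neither the 3 or 9 month activPAL wears will be followed by an in-person visit". Its clinic measurements belong to "assessments and measurements at in-person visit (baseline, 6 and 12 months". The Remote cohort (184 planned) repeats its baseline measurements, blood pressure included, by phone at month 3.

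On missing data: "If dropout is above 15%, we will employ imputation techniques to address missing data issues".

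**The concern.** Taken alone, the Aim 1 sentence could be coded as a GEE with a single group coefficient across both visits. That coefficient is a weighted average of the month-3 and month-6 differences, whereas the trial is designed around month 6. An effect that fades would be overstated as a 6-month result; one that builds would be understated and lose power. A visit main effect would not help, because it leaves the weights unchanged. With two models available, the choice might also be made after seeing the data.

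Blood pressure adds a second worry. All month-3 pressures come from the Remote cohort, so an average would bring in a visit that the Original cohort never had. Readings absent by design might also be counted toward the 15% imputation trigger: 100/284 = 35.2% of month-3 readings, or 100/568 = 17.6% of all readings at months 3 and 6.

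**Working it through.** **Inputs from the power paragraph and Section 4.a.** 284 randomised 1:1; 15% loss; SD of change 97 min/day (sitting), 14.7 mmHg (systolic), 9.5 mmHg (diastolic); differences 41, 6.2 and 4.0; cohorts of 100 and 184. **Assumed, not in the documents:** two-sided 0.05, between-visit correlation r of 0.3-0.7, equal SD and attrition at both visits, and every month-3 to month-6 effect path.

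**1. The plan's own figure.** 284 × 0.85 = 241.4, taken as 121 and 120. SE = SD × √(1/121 + 1/120) = SD × 0.1288, which gives 12.50, 1.894 and 1.224. The ratios of difference to SE are 3.28, 3.27 and 3.27. A noncentral t with 239 df gives power of 90.5% (sitting), 90.3% (systolic) and 90.2% (diastolic). The stated 90% is therefore that of a comparison at a single time point.

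**2. Weight of month 3 if one common effect were fitted.** For sitting, both cohorts contribute at both visits, so the weight is 1/2. For blood pressure, with 92 × 0.85 = 78.2 Remote and 50 × 0.85 = 42.5 Original per arm:

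- independence: 78.2/(78.2 + 120.7) = 0.393
- exchangeable: [78.2/(1+r)] / [2 × 78.2/(1+r) + 42.5] = 0.369, 0.355 and 0.342 for r = 0.3, 0.5 and 0.7

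**3. Consequence.** For sitting, the pooled estimate is (d3 + d6)/2 and the SE is multiplied by √((1+r)/2). For systolic pressure, the weights in step 2 are used with a robust variance.

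| Effect, month 3 → month 6 | Month-6 contrast | One common effect |
|---|---|---|
| Sitting 41 → 41 min | 41; power 90.5% | 41; 94-98% |
| Sitting 20.5 → 41 min | 41; 90.5% | 30.75; 76-86% |
| Sitting 41 → 20.5 min | 20.5; 37% | 30.75; 76-86% |
| Systolic 6.2 → 6.2 mmHg | 6.2; 90.3% | 6.2; 92-97% |
| Systolic 3.1 → 6.2 mmHg | 6.2; 90.3% | 5.0-5.1; 77-87% |

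The two models differ only when the effect changes between visits. The documents give no effect path.

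**4. Which model the plan describes.** The Purpose makes the same comparison of group means as Section 5.a and fixes it at 6 months. The outcomes table, the Aim 1 heading and the power paragraph agree. Aim 3 pairs month-3 mediators with month-6 outcomes, so it treats the month-6 outcome as a separate quantity. Section 5.a does not ask for a common or time-averaged effect. A GEE with group, visit and group-by-visit terms, reported at month 6, satisfies all of these places. A pooled coefficient fits the model sentence only when that sentence is read apart from its heading.

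**5. The imputation trigger.** Section 5.a uses the word dropout both in the preliminary analyses and in Aim 1, and the power paragraph applies the same 15% as loss to follow-up of participants (284 to 241). An Original-cohort participant with no month-3 pressure scheduled has not dropped out. The 35.2% and 17.6% count readings, which the plan does not do.

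**6. Mixed cohorts.** Each cohort is randomised between the same two arms, so a Remote-only month-3 comparison is still a randomised one. It could distort the result only if the effect differed by visit or cohort and a common effect were fitted.

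**The case for a change.** The strongest case for acting is that naming a time point does not name a coefficient. A primary analysis should leave one model standing, and the fix is a sentence that costs no participants and no power. The same gap passes to the secondary and exploratory outcomes, which are to use similar models. The power paragraph is also untidy: it ties 6 months explicitly to sitting only, and attaches the 241 observed to 12 months.

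Part of this stands. The term or contrast is not written out anywhere, the working correlation is not named, and month-3 blood pressure is Remote-only without Section 5.a saying so. But these omissions do not leave the target open, because the target is stated repeatedly, including in the heading above the model. The worry about choosing after the data are seen is limited, though not removed, by the plan's blinding of the statistician to intervention condition. The argument from the 15% trigger does not stand.

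**Conclusion.** No change follows. This is an incomplete model statement that an analyst would fill sensibly, because only a model reporting the month-6 difference agrees with every place where the plan describes Aim 1. The distortion in the table (30.75 instead of 41 minutes; 5.0-5.1 instead of 6.2 mmHg) needs both a common-effect model that the plan never specifies and an effect that differs between visits. If effects are equal, even that model is unbiased and more powerful. The month-6 contrast keeps the planned power of about 90% with 241 observed, assuming two-sided 0.05. The conclusion rests on reading Section 5.a together with the Purpose, the outcomes table, the Aim 1 heading and the power paragraph.
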